This design avoids the confounds present in many previous studies of treatment response. First, it holds treatment intensity constant while systematically measuring the effects of varying amounts of treatment. Second, it uses both between and within-subject design components to control for a variety of potential confounding effects, including social contact, inter-subject variability, and the passage of time. Third, it examines the relationship between psycholinguistic, cognitive, and neuroanatomical factors and treatment response. Previous studies of treatment response have examined the effects of only one of these factors in accounting for differential response to treatment.

C.1 Study participants

Potential participants will be informed of the study on the PIRATE website as well as during PIRATE candidates' initial evaluation to determine eligibility for PIRATE participation. PIRATE candidates will be informed that they may be eligible to participate in the study if they meet additional study eligibility requirements. As described below, study participants will receive up to \$1500 to defray any travel expenses incurred as part of study participation, to be pro-rated if they fail to complete all study procedures (including follow-up visits).

All study participants will be community-dwelling veterans with a positive diagnosis of aphasia and the ability to live independently and carry out activities of daily living during their PIRATE program participation. Aphasia diagnosis will be provided by the referring provider, based on performance on standardized aphasia-assessment measures such as the Comprehensive Aphasia Test (CAT), the Western Aphasia Battery, Revised (WAB-R), or the Boston Diagnostic Aphasia Exam (BDAE). Aphasia diagnosis will be verified by PIRATE staff prior to enrollment based on clinical impression and performance on the CAT, with a language modality mean T-score below the 70 being required for aphasia diagnosis. Although this criterion is more liberal than the cut-off score of 62.8 described in the CAT manual, our experience suggests that patients may score above this cut-off but nevertheless present with clinically significant naming impairments. Additional exclusionary criteria for PIRATE participation are listed in Table 5 below.

Inability to carry out activities of daily living necessary for self-care
Lack of physical independence
Significant mood or behavioral disorders
Drug or alcohol dependence

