Some participants may also have co-occurring conditions which would prevent them from participation in the imaging arm of the study (claustrophobia; presence of metal in the body). These participants will be enrolled in the study but will not complete imaging procedures. A chart review of PIRATE participants to date indicates that approximately 20% of veterans enrolled in PIRATE may have such exclusionary criteria: roughly 17% report pacemaker or other implanted metal objects or devices incompatible with MR scanning. Thus, the participant sample used to address the neuroanatomical hypotheses proposed under Specific Aim 1 may be smaller than the sample contributing data the other proposed analyses. Under the worst case scenario of no overlap between these imaging-related exclusionary criteria and those described in the preceding paragraph, we expect to obtain a sample size of 40 participants (50 minus 20%) to conduct the proposed imaging-related analyses. As described in section C.3.1.3 below, this sample size should be sufficient to detect the relationships relevant to the neuroanatomical hypotheses.

C.2 Procedures

The schedule of procedures for participants enrolling in the study is summarized in the flowchart in Figure 4. Participants enrolling in the research study will receive a single pre-treatment structural MRI and a battery of cognitive assessments at program entry (see section C.2.3 below). They will also have their performance on standardized measures of naming and other language functions assessed repeatedly throughout the protocol (see section C.2.2 below), and they will receive an intensive dose of a treatment (SFA) designed to target lexical-semantic processes (see section C.2.1 below). Participants' performance on treated and untreated lexical items will be probed three times weekly, to assess acquisition and generalization and to decide when participants will move to a novel set of treatment exemplars.

Half the participants will be randomly assigned to a delayed-treatment condition. The purpose of this condition is to provide an additional measure of experimental control, to ensure that any observed improvements are not due simply to the social contact afforded by the residential component of the treatment program. Previous work [7] has found that simple exposure or engagement in the absence of specific therapy

[figure not shown]

Figure 4: Testing and treatment procedures for study participants

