The following procedures will be implemented to monitor and ensure treatment fidelity. All treatment sessions will be video recorded. For each participant and each day of treatment, study staff not providing treatment will randomly select 15 minutes (~ 7% of total treatment time) of video and review it for adherence to the semantic feature analysis (SFA) protocol. All deviations will be discussed with the treating clinicians. Monitoring will occur and feedback will be provided to clinicians by the end of the business day following the monitored sessions. When monitoring of a given clinician-participant pair detects no more than one deviation on three consecutive days, the pair will be monitored weekly for the remainder of the 4-week session. If subsequent weekly monitoring reveals more than one deviation from the SFA protocol, daily monitoring will be re-instituted until the criterion for weekly monitoring is again reached.

Treatment and probe stimuli for study participants will consist of picturable nouns, consistent with methods used in existing SFA treatment studies. All pictures used as treatment and probe stimuli will be drawn from a subset of 361 of the 520 object pictures published by the UCSD Center for Research in Language International Picture Naming Project^[91]. These 361 pictures were selected by removing from the full set 159 picture stimuli that are also included in the Philadelphia Naming Test^[92], which will serve as a secondary outcome measure for Specific Aims 1 and 2. Participants will be asked to name this set of 361 pictures on three occasions across the two days of their initial evaluation, with all administrations separated by at least 5

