hours. All treatment and probe pictures will be selected from the pictures named correctly on fewer than two of those occasions. Four sets of 10 items each will be selected as potential treatment items, along with four sets of 10 related generalization probe items and four sets of 10 unrelated generalization probe items. For each treatment item, a category coordinate will be selected as a generalization probe item. The unrelated generalization probes will be selected from remaining items belonging to categories not occurring within the treatment set. These items will also be selected to minimize associative and other semantic relationships with items in the treatment sets. Within the constraints of semantic relatedness and baseline performance level, we will balance the treatment and generalization sets for lexical frequency and length.

[figure not shown]

Figure 5. Panel A: Expected score for each of the seven 25-item PNT alternate forms, compared to empirical data of 254 aphasic patients. Panel B: Mean Rasch-scaled score for each of the seven alternate PNT forms, for a subsample of 57 aphasic patients.

C.2.2 Probe stimuli, procedures and schedule

Following baseline assessment of all 361 UCSD CRL items, the 40 items selected for training, 40 related items, and 40 unrelated items will be probed at treatment initiation, three times per week during

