treatment, at program exit, and at one-month follow-up. As an additional measure of within-subject control, we will also obtain baseline measures and weekly probes on the non-word repetition subtest of the PALPA. Generalization of SFA treatment to improved performance on nonword repetition is theoretically possible, but unexpected. The Philadelphia Naming Test (PNT)^[92], a standardized measure of naming performance, will be administered weekly during baseline and treatment phases of the study. In order to eliminate the possibility that observed performance gains on the PNT could be attributed to repeated exposure to the same picture stimuli, we used methods based in item response theory^[93] (IRT) to organize the 175 PNT items into seven equivalent 25-item alternate forms. We accomplished this in the following steps, using data taken from the Moss Aphasia Psycholinguistics Project Database (MAPPD)^[94], which contains item-level PNT response data collected from 254 persons with aphasia. First, we confirmed that a single underlying factor can satisfactorily account for aphasic performance on the PNT. We fit a unidimensional model to the data using NOHARM^[95], and found that fit was excellent (root mean square of the model residuals = 0.010 vs. criterion of < 0.25; Tanaka Goodness of Fit Index = 0.985 vs. criterion of >0.95 for good fit). Next, we fit the data to a 1-parameter IRT model (Rasch) for dichotomous items using WINSTEPS^[96, 97]. We found that all items obtained information-weighted mean-square statistics <1.4, suggesting adequate fit to the model^[98]. We then used the model-estimated item difficulty values to construct the seven alternate forms such that they were of equivalent overall difficulty and gave equivalent expected proportion correct scores as a function of latent naming ability. Panel A of Figure 5 shows the model predicted and empirical raw score for each alternate form as a function of Rasch-scaled latent naming ability, estimated based on the responses to the full PNT. The model curves for the seven forms are essentially identical and well-approximated by the empirical data. We then cross-validated these forms using new data from a subsample of 57 patients who were administered the PNT a second time. For these 57 patients, we computed the latent naming ability score for each alternate form and found that they adequately fit a strictly parallel test model (i.e., had equivalent means, true score variances, and error variances), $\chi^2 = 37.757$ with 32 df, $p = 0.223$. The average correlation between forms was 0.87 (min-max = 0.82-0.93). The means and standard deviations for each of the seven forms are displayed in Panel B of Figure 5.

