Secondary dependent variables for these analyses will include accuracy on untreated related stimuli (accuracy at study exit minus accuracy at study entry) and Rasch-scaled scores for PNT stimuli (scores at exit minus scores at entry). Previous studies have not found any predictive relationships between neuroanatomical or other variables and generalization to untrained stimuli^[9, 20]. However, those studies did not administer treatment in the amounts or intensities provided in PIRATE or in the proposed research. It is possible that more intensive and/or larger doses of aphasia treatment may uncover stronger generalization effects (as well as stronger predictive relationships) than have previously been reported.

C.3.1.1 Group effects on treatment response

Participants will be classified as having primarily phonological, primarily lexical-semantic, or mixed naming impairments, using the methods described in section C.2.3 above. A between-participants analysis of variance will be carried out on the primary and secondary dependent measures of treatment response, with language-impairment group as an independent variable. As predicted by Hypothesis 1a and consistent with previous findings in the naming-treatment literature^[12, 44], we anticipate that there will not be a main effect of language-impairment group on treatment response. The different groups of naming-impaired individuals will show comparable benefit from intensive, semantically-oriented naming treatment. If group differences are found in the ANOVA, we will explore their source using Tukey's multiple comparisons to control type-I error.

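### C.3.2 reads rises on repeatedly named probe pictures as acquisition and generalisation, without comparing item types or using the nonword control series

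*Combined protocol and SAP*

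**What the plan says.** **Exposure.** Under C.2.1, "Participants will be asked to name this set of 361 pictures on three occasions across the two days of their initial evaluation". Treatment and probe items are then chosen from those pictures. C.2.2 says that the 40 training items, "40 related items, and 40 unrelated items will be probed at treatment initiation, three times per week during" the treatment weeks, with further probes when the program ends and about a month later. C.2 gives the purpose: performance on treated and untreated items "will be probed three times weekly, to assess acquisition and generalization".

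**Safeguards named.** For the PNT, C.2.2 builds seven alternate forms: "In order to eliminate the possibility that observed performance gains on the PNT could be attributed to repeated exposure to the same picture stimuli". It also adds a control task: "As an additional measure of within-subject control, we will also obtain baseline measures and weekly probes on the non-word repetition subtest of the PALPA". It regards generalisation to nonwords as possible in theory but not expected. Section C says that the between- and within-subject components serve "to control for a variety of potential confounding effects, including social contact, inter-subject variability, and the passage of time".

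**Analysis.** C.3.2 fits a multivariate mixed model with polynomial time contrasts to PNT, acquisition and generalisation scores from entry to exit, followed by Bonferroni-corrected comparisons of successive measurements. A positive linear trend is to be read as gain from the four weeks of treatment, and gains on untreated items as generalisation. In C.3.1 a secondary outcome is "accuracy on untreated related stimuli (accuracy at study exit minus accuracy at study entry", listed together with Rasch-scaled PNT change.

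**The concern.** The plan recognises that naming the same pictures repeatedly can raise scores, and it protects the weekly PNT against this. The probes repeat identical pictures three times a week with no such protection. They supply the Aim 1 primary outcome (treated items) and the probe-based measure of generalisation.

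The data that could help are collected. Related and unrelated items share one probe schedule, and nonword repetition is followed weekly. But C.3 specifies no treated-untreated or related-unrelated contrast, and nonword repetition appears in none of its analyses. At stake is what a rising probe curve in C.3.2 means. Without a series on the same schedule for comparison, a rise from treatment, from repeated naming or from time alone would be reported in the same way.

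**Working it through.** **1. Namings per untreated picture.** The documents state no total, so I count from the schedule.

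- Initial evaluation (C.2.1): 3
- Treatment initiation (C.2.2): 1
- During treatment: 3 per week × 4 weeks = 12
- Before the exit probe: 3 + 1 + 12 = 16
- Including a separate exit probe: 17 (16 if the last weekly probe serves as the exit probe)
- From the entry probe up to, but not including, exit: 1 + 12 = 13

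If the delayed group is also probed three times in its untreated week, which C.2.1 does not spell out, its counts become 19 and 20.

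**2. Series collected against series analysed.**

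| Series | Collected | Use in C.3 |
|---|---|---|
| Treated items | 3 per week | time trend and successive differences; change score |
| Related untreated | 3 per week | same, as generalisation probes |
| Unrelated untreated | 3 per week | not named separately; at most pooled under untreated or generalisation probes |
| Nonword repetition | weekly | none |
| PNT alternate forms | weekly | time trend and successive differences; change score |

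Every C.3.2 contrast described is a contrast over time. None is between item types.

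**3. Illustration of size.** The practice gain is my assumption, since the documents give none. The SDs are borrowed from treated items in the small prior studies in A.1.1, with four patients per group: 17 and 9 points, pooled √((17² + 9²)/2) = √185 = 13.6. Take n = 50 completers (C.1), no true generalisation and a mean practice gain g. A two-sided 5% paired t-test of entry-to-exit change has noncentrality g/(SD/√50). For g = 5 and SD = 13.6 this is 5/1.92 = 2.60 on 49 df. The probability of a significant rise is:

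| g (points) | SD 9 | SD 13.6 | SD 17 |
|---|---|---|---|
| 3 | 64% | 33% | 23% |
| 5 (2 of 40 items) | 97% | 72% | 53% |
| 8 | about 100% | 98% | 90% |

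This test stands in for the linear trend. The percentages do not apply to the one-week Bonferroni comparisons, where each step holds only part of the gain. If practice is the same for related and unrelated items, their difference has expectation g − g = 0 and keeps its 5% error.

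**4. Precision of the contrast.** With equal SDs and correlation ρ between the two changes, SD(related − unrelated)/SD(raw) = √(2(1 − ρ)). This is 1.18 at ρ = 0.3, 1.00 at ρ = 0.5 and 0.77 at ρ = 0.7. The documents do not give ρ.

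**The case against.** Several points on the other side stand, and they limit the concern.

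- **Unrelated items are not designated controls.** A reader might infer that the plan collected a control set and discarded it. C.2.1 calls these items generalisation probes, and A.1.1 cites 12 cases in which gains reached unrelated items. Only nonword repetition is called a control. Equal gains in related and unrelated items would fit practice or broad generalisation equally well.
- **Aim 1 is mostly insulated.** A reader might infer that the C.3.1 predictor findings are invalid. Those analyses are an ANOVA between impairment groups, regressions on cognitive factors and lesion mapping. A practice gain common to all participants cancels there. It would bias them only if it varied with the predictor, and the documents do not show that it does.
- **Acceleration is not explained by practice.** A reader might infer that repeated naming would produce the late rise predicted under Hypothesis 2b. Probing runs at a constant three per week, and the plan predicts opposite curvature for treated and untreated items on that one schedule. A shared practice curve does not by itself give that pattern.
- **Generalisation does not rest on the probes alone.** PNT change has alternate forms, and C.3.3 adds the CAT and connected speech.
- **Partial checks exist.** The delayed-versus-immediate model in C.3 includes untreated probes, and C.3.2 predicts no change from initial evaluation to entry. The first covers one week, at most about 3 namings against the 13 from entry up to exit, and a gain there would be put down to socialisation. The second precedes the treatment-period probing.

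Nonword repetition is a different task. It can check general change but not picture-specific practice.

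**Conclusion.** The concern holds for the mean-gain claims in C.3.2. Probe pictures are named 16 to 17 times by exit, no analysis compares item types, and the one series called a within-subject control is not analysed. Repeated naming or time could therefore be reported as a linear gain or as generalisation on the probes. How often depends on a practice effect that the documents do not give. Under the assumptions above, a 5-point effect would make raw change significant in 53% to 97% of trials.

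The documents do not support the wider reading that all generalisation evidence is compromised or that the design has no working within-subject control. PNT change is less exposed, and the delayed arm is a limited check. This is a worthwhile, inexpensive improvement to the analysis, and the treated-item primary outcome need not be redefined.

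**What to change.** **In C.3.2,** add item type (treated, related, unrelated) by time to the mixed model, with two named contrasts:

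- Treated versus untreated, for an item-specific treatment effect beyond repeated probe naming.
- Related versus unrelated, for generalisation specific to semantic relatedness.

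Define treated by whether the item's set has been introduced. Under C.2.1 a new set of 10 starts only when the criterion is met, so some of the 40 training items may go untrained.

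Analyse nonword repetition over time as the expected-no-change series for general change. Report raw gains and PNT change beside the contrasts, and state in advance that equal gains in related and unrelated items cannot separate practice from broad generalisation.

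**In C.3.1,** keep the change scores and add the contrasts only as a supplementary outcome.

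**Cost.** A few model terms and one further series, all on data already collected, with no added burden on participants. The downside is that true generalisation to unrelated items is netted out of the related-minus-unrelated contrast, which may also be less precise than raw change (it is when ρ is below 0.5). Reporting both deals with the first, and the second should be acknowledged.

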Pictorial input- word pairs	No cut-off	= 70% accuracy
Pictorial and verbal input	20% > pic. input-word pairs	= 70% accuracy
Pictorial input, field of 4 items	No cut-off; semantic foil errors predominate	= 70% accuracy
Picture naming		
Oral naming	= 60% of errors are semantic paraphasias, phonological accurate unrelated words, or no response; =40% are phonemic paraphasias	= 60% of errors are phonemic paraphasias, circumlocutions, or neologisms; = 40% are semantic paraphasias
Written naming	Same as above	Same as above
Phonemic cueing responsiveness		
First-sound cueing	No cut-off	Facilitative for = 15% of inaccurately named words Not responsive to miscues
Miscuing	May be responsive to miscues	
Oral reading and repetition		
Oral reading	= oral naming accuracy	No cut-off
Repetition	= 90% accuracy	< 90% accurate

Figure 6. Criteria for classification of patients' naming deficits, taken from Wambaugh et al.^[12]

The semantic categorization task will involve sorting of 70 pictures into seven different superordinate categories (e.g., transportation, animals, tools, etc.). Rhyming, repetition, word-picture matching, oral reading, and repetition will be assessed using appropriate PALPA subtests. Picture naming error type data will be collected from the initial presentation of the 361-picture set described below, and from the subset of 50 Philadelphia Naming Test items that each participant will receive by program entry, also as described below. Phonemic cueing responsiveness will be measured by presenting the pictures of the Boston Naming Test along with a single-segment phonemic cue. Those cues will either overlap with the first segment of the target (first sound cueing:

e.g., [b] for target 'broom') or will overlap with the first segment of a semantic competitor (miscueing: e.g., [m] for target 'broom,' overlapping with semantic coordinate 'mop')^[102].

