Study measures will be subjected to two sets of analyses which test the dose-response hypotheses relevant to Specific Aim 2. These analyses will compare the PNT scores and acquisition and generalization probe scores across the 4 weeks of PIRATE treatment, to determine the dose-response relationship and to identify the points of largest change in response to treatment. The last of the three weekly naming probes will serve as a measure of weekly acquisition and generalization performance. This will ensure that performance on PNT and naming-probe measures may be directly compared, as they will be on the same schedule.

First, the data for the PNT scores and the acquisition/generalization probes will be analyzed with a multivariate mixed model with polynomial trend contrasts. To simplify interpretation, only time points 2 through 6 (program entry through program exit) will be included in the trend analyses. These trend analyses will first test whether there is a linear relationship between time in treatment and treatment response for study measures, as predicted by Hypothesis 2a. Second, they will test whether acquisition and generalization probes show additional curvilinear relationships to time in treatment, as predicted by Hypothesis 2b. We anticipate that there will be a positive linear trend between program entry and program exit for PNT scores and for acquisition and generalization probes. This finding would indicate that the four weeks of treatment results in significant score gains. We further predict that the trend for acquisition probes will also have a significant curvilinear (quadratic or higher-order) component, consistent with decelerating improvement across the four weeks of treatment. This finding would indicate that the largest gains for specifically treated skills/items occur early in treatment, with declining gains in later weeks. Finally, we predict that the generalization probes will also demonstrate a curvilinear relationship to time, due to accelerating improvement across the four week program. This finding would indicate that the largest gains for related but untreated items occur late in treatment, emerging later than the gains for specifically treated forms.

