Second, six pairwise planned comparisons of scores across all seven consecutive measurement intervals will be carried out, using Bonferroni-corrected t-tests to maintain the familywise type-I error rate at 0.1. As predicted by Hypothesis 2a and consistent with the preliminary outcome data from PIRATE (see B.1.3 above), we anticipate that there will be a significant increase in both PNT score and acquisition/generalization probe performance for each additional one-week increment of treatment. We also predict non-significant changes between the initial evaluation and program entry and between program exit and follow-up.

In case a linear relationship is not found between time in treatment and outcome measures, additional analyses will be carried out examining the performance of different subsets of veterans. For example, veterans will be divided into groups based on their aphasia severity, since previous treatment findings have suggested that milder aphasia severity may be associated with less change on language-performance measures^[1]. Separate trend analyses will be carried out for the different severity groups, to examine whether different dose-response relationships may be observed for different aphasia groups.

In addition to these within-participant analyses examining dose-response relationships, a complementary set of between-participants analyses will be carried out, examining the effects of two versus four weeks of treatment for different randomly-selected groups of participants. It is standard practice in the dose-response literature to compare the response of groups exposed to different amounts of a therapeutic

agent, to see the incidence of positive or negative responses to the agent in the groups (e.g., frequency of remission or toxicity^[110]). These complementary between-participant analyses will simulate this comparison for the current study, providing an additional randomized-control measure of the effect of high dosage SFA on individuals with naming impairments. For these analyses, participants will be randomized to one of two groups. For half the participants, outcome measures (naming and PNT scores) will be sampled after two weeks' exposure, while for the other half, outcome measures will be sampled after the full four weeks of treatment. We anticipate that changes in study measures will be larger for the four-week group than for the two-week group.

C.3.3 Additional analyses of general language performance and connected speech

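### The PNT gain in Aim 1, a secondary outcome, starts from one 25-item form at entry although a second parallel pre-treatment form is collected; pooling the two is a cheap, modest gain in precision

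*Combined protocol and SAP*

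**What the plan says.** Section C.3.1 makes change on treated items the primary Aim 1 outcome. The PNT change, "Rasch-scaled scores for PNT stimuli (scores at exit minus scores at entry", is one of two secondary outcomes. It goes into the impairment-group ANOVA (C.3.1.1), the cognitive regressions (C.3.1.2) and the lesion mapping (C.3.1.3, also from program entry).

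Section C.2.2 describes how item response theory was used "to organize the 175 PNT items into seven equivalent 25-item alternate forms". The PNT "will be administered weekly during baseline and treatment phases of the study". On form quality it says: "The average correlation between forms was 0.87 (min-max = 0.82-0.93", and that the forms "adequately fit a strictly parallel test model (i.e., had equivalent means, true score variances, and error variances".

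Section C.2.3 mentions "the subset of 50 Philadelphia Naming Test items that each participant will receive by program entry", which is two forms. Section C.3.2 treats initial evaluation and entry as separate occasions: "only time points 2 through 6 (program entry through program exit) will be included in the trend analyses". It also states: "We also predict non-significant changes between the initial evaluation and program entry and between program exit and follow-up".

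**The concern.** On the plan's own premises, the initial-evaluation form and the entry form measure the same baseline: the forms are parallel and no change is expected between the two occasions. Yet the Aim 1 gain subtracts only the entry form. No section brings the earlier form into this outcome.

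A difference between two short forms is noisy. Noise in an outcome shrinks its correlation with cognitive factors and lesion measures and lowers power. It also makes the absence of a group difference, which Hypothesis 1a predicts, easier to obtain. The sample is limited to about 50, or 40 for imaging, so precision available from data already collected is worth using. Neither the sample-size argument in C.3.1.2 nor the power statement in C.3.1.3 considers the reliability of the PNT change score.

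**Working it through.** **Inputs from the documents**
- One form has 25 items; 175/25 = 7 forms (C.2.2).
- Two forms are given by entry: 50/25 = 2 (C.2.3).
- Mean inter-form correlation ρ = 0.87, range 0.82 to 0.93 (C.2.2).
- The initial evaluation is 4 to 6 weeks before entry (C.2).
- n = 50, or 40 for imaging (C.1).

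**Inputs assumed, because the documents do not give them**
- SD of true gain: 0.2 to 0.5 of the form SD.
- True correlation of a predictor with gain: 0.2 to 0.7.
- Two-sided α of 0.05.

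That the entry score is a single form is inferred from C.2.2, C.2.3 and C.3.2, because Figure 4 is not shown.

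**1. The plan's own power figure.** C.3.1.3 states power 0.80 for r = 0.38 at n = 40. With power = Φ(atanh(r)·√(n−3) − z), the result is 0.785 one-sided at 0.05 and 0.68 two-sided. The stated figure is therefore reproduced within 2 points by a one-sided test. At r = 0.65 power exceeds 0.99 either way, as stated. None of this is disputed here. The figure is for observed correlations and says nothing about change-score error.

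**2. Error variance of the gain.** Set the observed form variance to 1. Error per form is e = 1 − 0.87 = 0.13.
- One entry form: e + e = 0.26.
- Mean of two pre-treatment forms: e + e/2 = 0.13 + 0.065 = 0.195.
- Reduction: (0.26 − 0.195)/0.26 = 25%.

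At ρ = 0.82 the fall is 0.36 to 0.27, and at ρ = 0.93 it is 0.14 to 0.105; both are again 25%. The saving is a quarter rather than a half because the exit form keeps its own error.

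**3. Drift before entry.** If true individual change between initial evaluation and entry has SD d, half of it enters the pooled-baseline gain and adds d²/4. This treats the drift as unrelated to the true gain and to the predictors.
- d = 0.3: 0.195 + 0.0225 = 0.2175, a 16% reduction.
- d = 0.4: 0.195 + 0.04 = 0.235, a 10% reduction.
- Break-even: d²/4 = 0.065, so d = √0.26 ≈ 0.51.

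A drift that is the same for everyone shifts the mean gain but not the correlations.

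**4. Illustrative power.** With true-gain variance v, observed r = true r·√(v/(v + error variance)). Example: SD 0.3 gives v = 0.09. At true r = 0.6 the observed r goes from 0.6·√(0.09/0.35) = 0.304 to 0.6·√(0.09/0.285) = 0.337, and power at n = 50 from 0.58 to 0.67. The table gives the rise in power, in percentage points, at n = 50 with no drift.

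| Gain SD | Reliability of gain | r 0.2 | r 0.3 | r 0.5 | r 0.6 | r 0.7 |
|---|---|---|---|---|---|---|
| 0.2 | 0.13 → 0.17 | 0.9 | 2.0 | 5.6 | 7.8 | 9.8 |
| 0.3 | 0.26 → 0.32 | 1.4 | 3.2 | 8.0 | 9.5 | 9.3 |
| 0.4 | 0.38 → 0.45 | 1.7 | 3.8 | 7.8 | 7.4 | 5.1 |
| 0.5 | 0.49 → 0.56 | 1.7 | 3.9 | 6.3 | 4.7 | 2.2 |

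At n = 40 the same grid gives about 1 to 3 points for r 0.2 to 0.3 and 4 to 10 points for r 0.5 to 0.7.

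**The case against.** The strongest defence is that exit minus entry brackets the treatment interval exactly. The plan keeps the initial evaluation apart on purpose: it is left out of the trend analyses, and the interval to entry is tested as a no-treatment contrast. Pooling it into the baseline counts half of any individual change over the preceding 4 to 6 weeks as treatment response. This stands. The proposal trades some possible bias for precision; it does not correct an error.

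Predicting no significant change concerns the group mean, not the stability of individuals. The PICA pilot in B.1.2 is mixed: p = 0.118 with complete data, and p = 0.018 after mean replacement, a method the protocol says probably overstates baseline change. The 0.87 comes from forms taken from a single repeat administration in 57 database patients, so it carries no information on lasting change between occasions. Hence 25% is an upper bound.

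Three stronger readings are tempting, and the documents do not support them.
- A reader might infer that the first form is wasted. It is used for error-type classification (C.2.3) and for the baseline-interval comparison (C.3.2).
- A reader might infer a gain of 5 to 10 points of power across Aim 1. That size needs true correlations of about 0.5 to 0.7, in a single bivariate test that the plan does not run. The planned tests are an ANOVA, regressions on several components, and Brunner-Munzel lesion mapping with false-discovery control.
- A reader might infer that pooling makes the gain score reliable. With a gain SD of 0.3, the remaining error variance of 0.195 is still more than twice the true variance of 0.09.

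The delayed arm is a further complication. It spends an untreated week in residence before treatment, and C.2.1 does not make clear whether its entry score precedes or follows that week, or whether it has a third pre-treatment form.

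**Conclusion.** The point holds as a cheap improvement to a secondary outcome. Using both pre-treatment forms cuts the error variance of the PNT gain from 0.26 to 0.195 of the observed form variance, at most 25%, and still helps unless individual drift before entry has SD of about 0.51 form SDs or more. This rests on the plan's own parallel-form result and correlation, and on the inference that entry is one form. The effect on power depends on undocumented quantities: about 1 to 4 points at true r 0.2 to 0.3 and 2 to 10 points at 0.5 to 0.7 (n = 50, gain SD 0.2 to 0.5, no drift). These figures only illustrate what the planned ANOVA, regressions and lesion mapping might gain. Exit minus entry is a defensible definition, and the documents give no ground for saying that it invalidates any Aim 1 analysis.

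**What to change.** In C.3.1, define the PNT baseline for the Aim 1 predictor analyses as the Rasch person score from the initial-evaluation and entry forms together (50 items), and the gain as exit minus that baseline. State which occasion counts as entry for the delayed-treatment arm, and use the same two occasions in both arms. Apply the definition in the ANOVA, the cognitive regressions and the lesion mapping. Keep exit minus entry as a prespecified sensitivity analysis; a clear difference between the two would point to change before entry.

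The cost is a short amendment to the analysis text, including the delayed-arm definition. No new data are needed. The price is that half of any individual change in the 4 to 6 weeks before entry is counted in the gain. The C.3.2 dose-response analyses can stay as they are.
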